STATISTICAL ANALYSIS PLAN

A randomized, concurrent controlled trial to assess the safety and effectiveness of the Separator 3D as a component of the Penumbra System in the revascularization of large vessel occlusion in acute ischemic stroke

Protocol CLP4853

2/5/2013

Contents

1	Overview.....	4
2	Study Success Criteria.....	4
3	Sample Size.....	4
3.1	Non-inferiority Margin Evaluation.....	5
3.2	Effectiveness Sample Size Evaluation.....	5
3.3	Randomization Methods.....	6
3.4	Blinding.....	6
4	Interim Analysis.....	6
5	Analysis Populations.....	6
5.1	Definitions.....	6
5.2	Randomization Variables.....	7
6	Statistical Methods.....	7
7	Baseline Characteristics.....	7
8	Patient Disposition.....	8
9	Effectiveness Analysis.....	8
9.1	Primary Effectiveness Analysis.....	8
9.2	Secondary Effectiveness Analysis.....	8
9.3	Handling of Multiplicity.....	9
9.4	Effectiveness Subgroup Analysis.....	9
10	Safety Analysis.....	10
10.1	Primary Safety Analysis.....	10
10.2	Secondary Safety Analysis.....	10
10.3	Analysis of Adverse Events.....	10
10.4	Handling of Multiplicity.....	11
10.5	Analysis of Deaths.....	11
11	Pooling Across Centers.....	11
12	Lost to Follow-Up and Missing Data.....	12
13	Committees.....	12
13.1	Clinical Events Committee/Data Safety Monitoring Board (CEC/DSMB).....	12

13.2	Core Lab	12
14	Changed to Planned Analyses.....	12
15	References	13

1 Overview

This is a 90-day multi-center, randomized, single blind study designed to evaluate the effectiveness and safety of the Penumbra System versus the Penumbra System with Separator 3D in the treatment of adult patients with acute ischemic stroke from large vessel occlusion in the cerebral circulation.

Approximately 230 adult patients will be enrolled from approximately 50 centers. Each site will be limited to a maximum enrollment of approximately 45 patients (~20% of total enrollment).

Patients will be randomized 1:1 to receive one of the following:

- Penumbra System (control);
- Penumbra System with Separator 3D (3D).

This Statistical Analysis Plan (SAP) will provide details to further elaborate statistical methods as outlined in the protocol and will describe analysis conventions. The SAP will be signed off prior to database lock.

2 Study Success Criteria

The study will be considered a success if the primary effectiveness non-inferiority criterion is met.

Primary Effectiveness Non-Inferiority: The proportion of patients in the Penumbra System with Separator 3D group who experience TICI 2/3 is no more than .15 below the proportion of patients in the Penumbra System group who experience TICI 2/3.

Additional analyses conducted for secondary endpoints and subgroups will be presented, but not utilized in evaluating the study success or Penumbra System product claims.

3 Sample Size

Approximately 230 patients are to be randomized in a 1:1 ratio to the Penumbra System group (115 patients) or the Penumbra System with Separator 3D group (115 patients).

3.1 Non-inferiority Margin Evaluation

The primary efficacy analysis will be performed by comparing the lower bound of a one-sided, 95.0% confidence interval, calculated using normal approximation, for the observed difference between the Penumbra System with Separator 3D and the control on the percentage of subjects that have a post procedure score of TICl 2-3 with a pre-specified non-inferiority margin (-15%). Should the lower limit of this difference be $> -15\%$, it can be concluded that the Penumbra System with Separator 3D is non-inferior to the control with respect to the primary efficacy measure.

3.2 Effectiveness Sample Size Evaluation

The sample size calculations assume that 80% of the standard Penumbra System patients experience success (TICl of 2 to 3) and 80% of the Penumbra System with Separator 3D patients experience success. Based on a binomial non-inferiority analysis with a non-inferiority margin of 15%, a study of 103 patients per group will have 85% power with a one-sided alpha of 0.05. The sample size was adjusted to 115 patients per group to account for up to 10% attrition rate.

Assuming that both the 3D arm and the control arm observe a rate of 80% (82/103), the 95% confidence interval for the difference between groups is (-11.0%, 11.0%). The sample size was calculated for a two-group, one-sided test for two proportions using the normal approximation to the binomial using SAS v 9.2 (SAS Institute, Cary, NC). The output of the proc power procedure for a Pearson Chi-square Test for Two Proportions is provided below.

Computed N Total	
Actual Power	N Total
0.852	206

The sample size calculations support enrolling a total of 230 patients (Table 1).

Table 1. Effectiveness Sample Size Parameters

Penumbra System Success Proportion	0.8
Penumbra System with Separator 3D Success Proportion	0.8
Enrollment Ratio (Control: 3D)	1:1
Power	85%
Alpha	0.05
Number of Sides	1

Null Proportion Difference	-0.15
Sample Size	206 (103 per group)
Estimated Attrition	10%
Total Sample Size	230 (115 per group)

3.3 Randomization Methods

Patients who are eligible based on inclusion and exclusion criteria and have had all pre-randomization screening procedures performed will be randomized by center in a 1:1 ratio to one of following two treatment groups:

- Penumbra System group (control)
- Penumbra System with Separator 3D group (3D)

The interactive voice response (IVRS) will be used to determine the randomization of patients. The IRVS vendor statistician will provide the randomization schedule. The Penumbra Inc. statistician will review the randomization schedule. Detailed instructions for using the IVRS will be provided to center personnel.

3.4 Blinding

The Penumbra Inc. clinical team responsible for the conduct of the study, the investigator, and center study personnel will not be blinded to each patient's randomized treatment group throughout the course of the study. The study subjects and the Core Laboratory will be blinded to treatment assignment.

4 Interim Analysis

No interim analyses are planned for the purpose of stopping the study early.

5 Analysis Populations

5.1 Definitions

All primary and secondary effectiveness endpoints will be performed for both the intent-to-treat (ITT) population and per-protocol (PP) population.

The ITT population will consist of all patients who signed the informed consent and are randomized in the study. The data from the ITT population will be analyzed by the treatment group assignment given at the time of randomization, even if the subject does not receive the correct treatment, or does not follow the protocol until completion. All randomized patients will

be followed and assessed for 90 days post-procedure, even when no neurothrombectomy is performed.

For the PP analysis, only patients who actually received the assigned treatment and do not have major protocol violations will be included.

For the safety analysis, patients will be analyzed according to the treatment they received.

Any treated patients who are not randomized through the IVRS system will be excluded from all analyses. The reason(s) for their exclusion from the study will be recorded. Listings will be provided for these patients, and they will be discussed in the clinical report.

Roll-in patients will be followed for 90 days and their safety will be summarized separately in the clinical report.

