3.3 Enrollment

Each center will have two roll-in cases prior to actual enrollment. These patients will not be part of the trial but will be followed for 90 days for safety. Prior to enrollment into the study, each patient will undergo an angiographic determination of the suspected vascular occlusion. Perform an arterial access procedure using standard percutaneous technique.

Perform a digital subtraction angiography (DSA) to define the angio-architecture of the occluded vascular segment. While a DSA to define the angio-architecture of the occluded vascular segment is preferred, CTA or MRA is an acceptable substitute. When possible, an assessment of collateral blood flow by DSA should be done per institutional standard of care, particularly in cases of terminal internal carotid artery occlusion.

If the occlusion is in a treatable vessel, position an appropriate guide catheter and advance the Penumbra Reperfusion Catheter into the occluded target vessel and the patient will be randomized to one of the following arms:

- 1) The Penumbra Separator 3D with the Penumbra System, or
- 2) The Penumbra System without the Separator 3D.

The randomization code will be obtained from a system provided by a vendor. A patient is considered enrolled once a treatment arm is assigned from the randomization system.

All patients will be assessed for a period of 90 days from randomization.

Randomized patients who were excluded for angiographic reasons will be followed for 90 days. The reasons for not including these patients will be captured in the Case Report Forms.

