3.4 Procedure Preparation for the Penumbra System

Procedure should be consistent with those listed in the *Instructions For Use* for each device. Refer to Warnings, Precautions, and Potential Adverse Events in the *Instructions For Use* for each device prior to use. However, for the purpose of this study, the Penumbra Separator 3D System should be used first for the revascularization of the target vessel if the patient was randomized to the Penumbra Separator 3D arm, to be followed by other components of the Penumbra System if necessary at the discretion of the investigators. The exception is the use of the 054 or 041 separators in the Separator 3D arm. Use of these devices in this arm will be considered a protocol deviation. Similarly, use of the Separator 3D in the control arm will be considered a protocol deviation.

- 3.4.1 As each device of the Penumbra System is used, remove the device from the packaging, and inspect for damage or for kinks.
- 3.4.2 Prepare Penumbra System devices for use by flushing the packaging hoop and device with heparinized saline (includes Penumbra Reperfusion Catheter and Penumbra Separator only).
- 3.4.3 Prepare a guide catheter or long femoral sheath according to the manufacturer's *Instructions for Use*.
- 3.4.4 Place the guide catheter or long femoral sheath into the appropriate cerebral artery that is proximal to the thrombus occlusion site.

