9.4 Safety

The denominator for the safety analyses is all enrolled patients who received the assigned treatment in the target vessel.

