10.1 Primary Safety Analysis

The primary safety endpoint is the proportion of patients with a device or procedure related SAE within 24 hours post-procedure. The proportion of patients in each group who meet the safety endpoint based on this criterion will be calculated.

The primary null hypothesis for safety in this study is that there is no difference in device-related and procedure-related serious adverse event rates. This null hypothesis will be tested against the alternative hypothesis that there is a difference between the two treatment groups. The null hypothesis will be rejected at the two-sided significance level of $\alpha = 0.05$. The primary analysis is an analysis of all patients according to treatment received. The Fisher's Exact test will be employed to assess the primary safety endpoint.

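### Safety and mortality are compared by an undefined treatment received, and protocol 9.4 sets a different denominator, so a failed Separator 3D attempt can stay in 3D, move to control or drop out

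*SAP*

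**What the plan says.** **Assignment rule in the SAP.** Section 5.1: "For the safety analysis, patients will be analyzed according to the treatment they received". Section 10.1, on device- or procedure-related serious adverse events within 24 hours: "The primary analysis is an analysis of all patients according to treatment received". Section 10.2 lists all-cause mortality and symptomatic intracranial haemorrhage as secondary safety variables, so the 5.1 rule reaches them too. Section 10.5 adds Kaplan-Meier and log-rank methods for death and names no other population. Nowhere is it said what makes the Separator 3D received: introduced, unsheathed, or used with aspiration.

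**Denominator in the protocol.** Section 9.4: "The denominator for the safety analyses is all enrolled patients who received the assigned treatment in the target vessel".

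**The two treatments.** Protocol 3.3 describes control only as "The Penumbra System without the Separator 3D". In the 3D arm, protocol 3.4 has the Separator 3D used first, "to be followed by other components of the Penumbra System if necessary at the discretion of the investigators", with a limit: "The exception is the use of the 054 or 041 separators in the Separator 3D arm". It continues: "Use of these devices in this arm will be considered a protocol deviation". Section 3.6.10 allows further separators after the 3D without repeating that limit. In the other direction, "use of the Separator 3D in the control arm will be considered a protocol deviation".

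**Follow-up.** SAP 5.1 has every randomised patient followed for 90 days, whether or not thrombectomy is performed.

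**The concern.** Using the Separator 3D takes several steps. It is inserted at protocol 3.6.5 and unsheathed at 3.6.7. A procedure can stop between the two and go on with other Penumbra components, and the plan does not say which safety group that patient belongs to.

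The documents give some reason to expect such cases. Protocol section 1 says the Separator 3D is compatible with catheters of at least 0.041 inch distal inner diameter. Table 5 lists the 032 and 3MAX catheters (0.032 and 0.035 inch in Table 3) for 2.5 to 3.0 mm vessels. Those passages need reconciling; I infer no failure rate from them.

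A difficult delivery is a plausible setting for a device- or procedure-related event. If that patient is moved to control or dropped, the event leaves the arm whose device was being tried. The reverse also occurs: under an as-treated rule, a control patient given the 3D as a last step moves to 3D and takes any later death along. Both movements depend on how the procedure went, so they undo the randomised comparison.

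SAP 3.4 leaves investigators, centre staff and the sponsor's clinical team unblinded, and the SAP need only be signed before database lock. Without a written definition, the label could be settled after the outcome is known.

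**Working it through.** **Inputs from the documents.** There are 115 patients per arm (SAP 3.2; 103 / 0.90 = 114.4, rounded up to 115, which reproduces the plan). The background rate is b = 3.2%, the serious procedural complication rate that protocol section 1 gives for the earlier single-arm study. It is not the same endpoint and serves only as illustration. The plan gives no figure of its own for the safety comparison.

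**Assumptions.** The documents give neither f, the fraction of the 3D arm attempted but not deployed, nor r, the event risk in those patients. I take f from 3% to 8% and r from 10% to 25%. Deployed 3D patients are first given the control rate b.

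**Difference, 3D minus control:**
- Kept in 3D: [(1 - f)b + f r] - b = f(r - b)
- Moved to control: b - (b + f r)/(1 + f) = -f(r - b)/(1 + f)
- Dropped: b - b = 0

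| f | r | Kept | Moved | Dropped |
|---|---|---|---|---|
| 3% | 10% | +0.20 | -0.20 | 0 |
| 5% | 15% | +0.59 | -0.56 | 0 |
| 8% | 25% | +1.74 | -1.61 | 0 |

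(Percentage points.) Middle row: 0.05 × (0.15 - 0.032) = 0.0059, and 0.0059 / 1.05 = 0.0056.

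**Limits of the sign change.** If r = b, the rule makes no difference. At b = 10% (assumed), the first row shows no shift and the middle row becomes +0.25 and -0.24. If deployed 3D carries its own excess d, the moved difference is d - f(r - b)/(1 + f). In the middle case, a non-negative d below 0.56 points is needed for the sign to change.

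**Whole patients, with deliberately higher event risk.** Assume 4 events per arm apart from the failed attempts.

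| Failed attempts (events) | Kept in 3D | Moved to control | Dropped |
|---|---|---|---|
| 3 (1) | 5/115 vs 4/115, +0.9, p = 1.0 | 4/112 vs 5/118, -0.7, p = 1.0 | 4/112 vs 4/115, +0.1, p = 1.0 |
| 6 (3) | 7/115 vs 4/115, +2.6, p = 0.54 | 4/109 vs 7/121, -2.1, p = 0.55 | 4/109 vs 4/115, +0.2, p = 1.0 |
| 12 (6) | 10/115 vs 4/115, +5.2, p = 0.17 | 4/103 vs 10/127, -4.0, p = 0.27 | 4/103 vs 4/115, +0.4, p = 1.0 |

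(3D vs control, points, two-sided Fisher's exact test.) The reading changes the direction of the estimate; in none of these cases does the test reach significance.

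**The case against.** A reader might infer that a patient whose 3D could not be deployed has received exactly the control treatment, so that the plan books the harm against control. The documents do not support that. No passage says an attempted 3D was not received, and attempted use fits the word at least as well. A patient in whom a 3D was introduced has not plainly been treated without it. The later care also differs: protocol 3.4 makes 041 and 054 separators a deviation in the 3D arm only, although 3.6.10 leaves that text mixed. Under protocol 9.4 the patient would be excluded, not relabelled. This objection stands, and the point is limited accordingly.

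Other points also carry weight:
- The size rests on assumed f and r. The f and r ranges above amount to roughly 3 to 9 patients and 0.3 to 2.3 events, and the comparison is not significant under any reading.
- Study success rests on effectiveness alone (SAP section 2), and SAP 10.4 treats safety comparisons as secondary.
- The CEC/DSMB adjudicates causality, and serious events are tabulated by subject, so a 3D-related event listed under control would be visible. That does not correct the between-arm comparison.
- Control-to-3D crossovers could partly offset the shift, though not predictably.

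What remains is that the documents permit three outcomes for the same patient, and that neither stated rule preserves randomisation, even for mortality.

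**Conclusion.** The point holds as a matter of an undefined term, two rules that disagree, and a non-randomised comparison where a randomised one is available. A failed 3D attempt can be kept, moved or dropped. The last two remove its harm from the 3D arm, and moving it can change the sign of the estimated safety difference: +0.6 versus -0.6 points at 5% undeployed, 15% risk and a 3.2% background, with deployed 3D assumed equal to control. The range over the f and r grid is +0.2 versus -0.2 up to +1.7 versus -1.6 points. I have no basis in the documents for a mortality figure.

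The consequence is the reported direction of a primary safety endpoint and of 90-day mortality. It is not a significant result in these illustrations, and it does not touch the success decision. The change is still worth making, because the randomised comparison costs almost nothing: all randomised patients are already followed for 90 days, and SAP 9.4 already runs the safety subgroup models on the intent-to-treat population.

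**What to change.** 1. **Mortality (SAP 10.2, 10.5):** compare by randomised arm in all randomised patients, using the 90-day follow-up already required. Take day 0 as randomisation, as protocol 9.4.2 does; SAP 10.5 uses the procedure date.
2. **Primary 24-hour serious adverse event comparison (SAP 5.1, 10.1):** report it by randomised arm in all randomised patients alongside the as-treated analysis. In the as-treated analysis, count as 3D any patient in whom a Separator 3D was introduced into the catheter or microcatheter, deployed or not. Show control-to-3D crossovers separately, since this definition would otherwise place them in 3D unseen.
3. **Protocol 9.4:** reconcile it with SAP 5.1 and 10.1 so that failed attempts are not excluded.

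The cost is one extra safety table, revised SAP and protocol wording, and a derivation from device-use records. Protocol 5.7 already requires device disposition by patient number. The case report form is not among the documents, so the sponsor should confirm that it captures introduction without deployment. No patients, visits or treatment rules change.

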5.2 Randomization Variables

The randomization of the study will be stratified based on the following:

- Clinical study center

6 Statistical Methods

Summary tables (descriptive statistics and/or frequency tables) will be provided for all baseline variables, effectiveness variables, and safety variables, as appropriate. Continuous variables will be summarized with descriptive statistics (n, mean, standard deviation, range, and median). Frequency counts and percentage of patients within each category will be provided for categorical data.

7 Baseline Characteristics

Baseline data will be analyzed to assess the comparability of treatment groups. Baseline data including, but not limited to demographics, clinical characteristics, and baseline vessel characteristics will be summarized using descriptive statistics. Differences between the treatment groups and their 95% confidence intervals will be calculated. Statistical testing will be performed as appropriate.

8 Patient Disposition

The number of patients for each of the following categories will be summarized.

- Randomized patients
- Patients completing the study; patients not completing the study
- Patients included in the intent to treat population
- Patients included in the per protocol population
- Patients included in the safety population

9 Effectiveness Analysis

9.1 Primary Effectiveness Analysis

The primary effectiveness variable is the proportion of patients with a post procedure TICl score of 2 to 3. The proportion of patients in each group who are successful based on this criterion will be calculated. The Core Laboratory data supersede the investigator-reported data in all analyses of TICl scoring.

For those patients who are treated with IA tPA or other non-FDA-approved treatments for the purpose of reducing the clot burden, their TICl score will be analyzed as a treatment failure (i.e. TICl 0 to 1) for the primary effectiveness analysis.

The primary effectiveness analysis will be the difference between the Penumbra System only group (control) and the Penumbra System with Separator 3D group. A binomial comparison will be used to test the one-sided null hypothesis that the difference in proportions is less than or equal to -0.15 ($H_0: P_{3D} - P_{Control} \leq -0.15$) vs. the alternative ($H_1: P_{3D} - P_{Control} > -0.15$). This is equivalent to evaluating that the lower bound of the 90% confidence interval for the difference is above 15%. The primary effectiveness analysis will be performed on the Per Protocol (PP) subject population. The analysis based on the Intent-To-Treat (ITT) population will be considered as supportive.

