9.3 Effectiveness

9.3.1 Primary Endpoint

The primary effectiveness variable is the proportion of patients with a post procedure TICI score of 2 to 3. The proportion of patients in each group who are successful based on these criteria will be calculated. The Core Laboratory data supersede the investigator-reported data in all analyses of TICI scoring.

The primary effectiveness analysis will be the difference between the Penumbra System only group (control) and the Penumbra System with the Separator 3D group. A binomial comparison will be used to test the null hypothesis that the difference in proportions is less than or equal to $-.15$ ($H_0: P_{3D} - P_{Control} \leq -.15$) vs. the one-sided alternative ($H_1: P_{3D} - P_{Control} > -.15$). This is equivalent to evaluating that the lower bound of the 90% confidence interval for the difference is above -15% .

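### SAP 9.1 states the primary non-inferiority threshold as +15% instead of -15%, a rule that a truly non-inferior device would almost never meet

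*SAP*

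**What the plan says.** SAP 9.1 defines the primary effectiveness comparison as the difference in TICI 2-3 proportions, 3D minus control. It tests the "one-sided null hypothesis that the difference in proportions is less than or equal to -0.15" against the alternative that the difference exceeds -0.15. The next sentence turns this into a confidence-interval rule: "This is equivalent to evaluating that the lower bound of the 90% confidence interval for the difference is above 15" per cent.

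The rule appears in four other places, each time with the threshold at minus 15 points:

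- **Protocol 9.3.1** has almost the same sentence, but requires the "lower bound of the 90% confidence interval for the difference is above -15" per cent.
- **SAP 2**, which makes this criterion the sole determinant of study success, requires that the 3D proportion "is no more than .15 below the proportion of patients in the Penumbra System group who experience TICI 2/3".
- **SAP 3.1** compares the lower bound of a one-sided 95% interval "with a pre-specified non-inferiority margin (-15"%), and concludes non-inferiority if the bound lies above that value.
- **SAP 3.2, Table 1** lists the null proportion difference as -0.15.

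**The concern.** The sentence in SAP 9.1 claims an equivalence that is false. A lower bound above +15% does not restate the non-inferiority hypothesis. It is a rule for superiority by more than 15 points.

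An analyst programming the primary analysis would naturally work from SAP 9.1. Applied literally, its interval rule would fail a device that is truly non-inferior, and would fail one that is moderately better. There is also a timing risk. If the contradiction is noticed only after results are known, correcting the success threshold could look like a post-hoc change, however obvious the intent.

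**Working it through.** **Inputs**

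- Control success rate 0.80: "The sample size calculations assume that 80% of the standard Penumbra System patients experience success" (SAP 3.2).
- 3D success rate 0.80: "80% of the Penumbra System with Separator 3D patients experience success" (SAP 3.2).
- Margin 0.15, one-sided alpha 0.05, 103 patients per group, 115 after 10% attrition (SAP 3.2).
- Interval by normal approximation (SAP 3.1). The lower limit of a two-sided 90% interval and that of a one-sided 95% interval are the same number; both use z = 1.645.

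**1. The plan's own figures**

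- SE = sqrt(2 × 0.80 × 0.20 / 103) = 0.0557.
- Power = Φ(0.15 / 0.0557 - 1.645) = Φ(1.046) = 0.852. The SAP prints 0.852.
- Attrition: 103 / 0.90 = 114.4, rounded up to 115. This agrees with the SAP.

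The sample size was therefore built on a threshold of -15%.

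**2. What each rule tests**

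Let d be the observed difference, 3D minus control.

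- Rejecting a true difference of -0.15 or less requires (d + 0.15) / SE > 1.645, which is d - 1.645 × SE > **-0.15**.
- The sentence in SAP 9.1 requires d - 1.645 × SE > **+0.15**, which rejects a true difference of +0.15 or less.

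These are different hypotheses, 30 percentage points apart.

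**3. Probability of meeting each rule**

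Exact enumeration of all binomial outcomes, 103 per arm, control rate 80%:

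| True 3D rate | Lower bound above -15% | Lower bound above +15% |
|---|---|---|
| 65% | 0.051 | 5 × 10⁻¹¹ |
| 80% | 0.852 | 8.2 × 10⁻⁶ |
| 85% | 0.984 | 0.0002 |
| 90% | 0.9997 | 0.004 |
| 95% | 1.000 | 0.0475 |
| 98% | 1.000 | 0.167 |
| 100% | 1.000 | 0.313 |

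Under the -15% rule, the 65% row is the type I error at the margin (about 0.05) and the 80% row is the planned power. Both match the SAP. Under the +15% rule, success at the design assumption has a probability of about 1 in 120,000. With 115 per arm, the two probabilities at 80% in both arms are 0.887 and 3.8 × 10⁻⁶.

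**4. The SAP's own illustrative result, 82/103 in both arms**

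- 82/103 = 0.796, and SE = sqrt(2 × 0.796 × 0.204 / 103) = 0.0561.
- The 95% half-width is 1.96 × 0.0561 = 11.0%, as in SAP 3.2.
- The 90% lower bound is -1.645 × 0.0561 = -9.2%. This passes -15% and fails +15%.

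**5. What would be needed if control observes 82/103**

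- Under -15%, 77/103 in the 3D arm is enough (difference -4.9%, lower bound -14.5%).
- Under +15%, no result is enough. With 103/103 in the 3D arm, d = 21/103 = 20.4% and SE = sqrt(0.796 × 0.204 / 103) = 0.0397, so the lower bound is 0.204 - 1.645 × 0.0397 = 13.9%.
- With 103/103 in the 3D arm, the +15% rule can be met only if control has 80/103 or fewer successes.

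**The case against.** The strongest reply is that nobody would apply the sentence as written. It only restates a test whose hypotheses are given correctly just before it. The success criterion is set correctly in SAP 2, the interval rule in SAP 3.1 and the null difference in Table 1, and the protocol has the sign right. On this view it is an editorial slip, and the contrast between 0.852 and 8 in a million describes a rule that will not be used. The +15% rule is also not strictly impossible: it succeeds 31% of the time if the true 3D rate is 100%. Finally, the minus sign might have been lost in reading the PDF, since the SAP text shows other character-level errors, such as variant spellings of TICI.

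Much of this stands. The intent is not in doubt, and margin, alpha, power and sample size are untouched. The near-impossibility of the +15% rule is conditional: it holds at the design assumption and for 3D rates up to about 90%. A lost character cannot be fully excluded, but minus signs survive in the same paragraph of SAP 9.1 and in SAP 3.1 and 3.2, and a look at the signed document settles it.

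None of this makes the sentence right. The text that defines the primary analysis contradicts itself on the decision threshold, and a reader should not have to choose between two versions by inference.

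**Conclusion.** The point holds. SAP 9.1 gives the interval form of the primary decision rule with the wrong sign, in conflict with its own hypotheses, with SAP 2, 3.1 and 3.2, and with Protocol 9.3.1. At the design assumption (80% in both arms, 103 analysed per arm, normal-approximation interval), the sign takes the probability of success from 0.852 to 8.2 × 10⁻⁶. With control at 80%, the +15% rule gives 0.004 at a true 3D rate of 90% and about 0.05 at 95%.

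The cause is most likely typographical, and the design is sound once the sign is corrected. It must still be fixed, because it concerns the threshold for the only criterion that determines study success. The practical risk is a contradictory governing text rather than a near-certain wrong analysis.

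**What to change.** In SAP 9.1, change the threshold in the confidence-interval sentence from 15% to -15%. It then agrees with the hypotheses in the same paragraph, with SAP 2, 3.1 and 3.2, and with Protocol 9.3.1. Check the signed SAP first, in case the minus sign is present there.

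The cost is one character. No change to sample size, margin, alpha or protocol is needed. SAP 1 has the plan signed off before database lock, and the correction should be made by then. If the SAP has already been signed, issue a revised SAP, as SAP 14 allows, before the primary results are known.
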